### 4.3 Exclusion Criteria

Subjects who meet any of the following criteria are not eligible for the study:

1. Life expectancy <6 months
2. Bleeding disorder other than congenital fibrinogen deficiency, including dysfibrinogenaemia
3. Prophylactic treatment with a fibrinogen concentrate
4. Treatment with:
  - Any fibrinogen concentrate or other fibrinogen-containing blood product within 2 weeks prior to start of treatment for the PK phase, a bleeding episode, or surgery
  - Any coagulation-active drug (i.e., non-steroidal anti-inflammatory drugs, warfarin, coumarin derivatives, platelet aggregation inhibitors) within 1 week prior to start of the PK phase or treatment for the bleeding episode or surgery, or as a planned or expected medication during the time period from Day 1 until 24 hours (i.e., 1 day) after the last *Octafibrin* infusion

5. Presence or history of:
  - Hypersensitivity to study medication
  - Deep vein thrombosis or pulmonary embolism within 1 year prior to start of treatment for the bleeding episode or surgery
  - Arterial thrombosis within 1 year prior to start of treatment for the bleeding episode or surgery
  - Hypersensitivity to human plasma proteins
  - Oesophageal varicose bleeding
  - End-stage liver disease (i.e., Child-Pugh score B or C)
6. Known positive HIV infection with a viral load  $>200$  particles/ $\mu$ L or  $>400,000$  copies/mL
7. Polytrauma 1 year prior to start of treatment for the bleeding episode or surgery
8. Diagnosis or suspicion of a neutralising anti-fibrinogen inhibitor currently or at any time in the past
9. Acute or chronic medical condition which may, in the opinion of investigator, affect the conduct of the study, including subjects receiving immune-modulating drugs (other than anti-retroviral chemotherapy), such as alpha-interferon, prednisone (equivalent to  $>10$  mg/day), or similar drugs, at study start
10. Treatment with IMP in another interventional clinical study currently or during the past 4 weeks

**NOTE:** If the period between screening and treatment or between treatments is more than 3 months, informed consent will be re-reviewed and confirmed prior to treatment, and details of the review process will be recorded in the patient chart and indicated in the CRF by the investigator. Also, inclusion/exclusion criteria will be confirmed prior to treatment.

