  - Bleeding disorder other than congenital fibrinogen deficiency
  - End-stage liver disease (i.e., Child-Pugh-score B or C)
  - Suspicion of an anti-fibrinogen inhibitor as indicated by previous IVR, if available  $<0.5$  (mg/dL)/(mg/kg)

- Treatment with any fibrinogen concentrate or other fibrinogen-containing blood product within 2 weeks prior to start of treatment for the bleeding episode.
- Did not use any coagulation-active drug (i.e., non-steroidal anti-inflammatory drugs, warfarin, coumarin derivatives, platelet aggregation inhibitors) within 1 week prior to start of treatment for the first bleeding episode, or as a planned or expected medication during the time period from Day 1 until 24 hours (i.e., 1 day) after the last *Octafibrin* infusion

Bleeding analysis set (BLEED): all documented bleeding episodes treated with *Octafibrin* in subjects of the FAS.

Bleeding per protocol analysis set (BLEED-PP): all documented bleeding episodes with no major protocol deviations, i.e. fulfilling the following conditions:

- Fully documented haemostatic efficacy data available for the bleeding
- $\geq 90\%$  of the planned total dose of the IMP was given for the bleeding
- $\geq 80\%$  of the calculated dose (if no dose was calculated, 0% will be assumed) of the IMP was given over all further infusions of the bleeding according to the treatment schedule
- The patient with the respective bleeding did not meet any of the following exclusion criteria:
  - Bleeding disorder other than congenital fibrinogen deficiency
  - End-stage liver disease (i.e., Child-Pugh-score B or C)
  - Suspicion of an anti-fibrinogen inhibitor as indicated by previous IVR, if available  $<0.5 \text{ (mg/dL)/(mg/kg)}$
  - Treatment with any fibrinogen concentrate or other fibrinogen-containing blood product within 2 weeks prior to start of treatment for the bleeding episode.
- The patient with the respective bleeding did not use any coagulation-active drug (i.e., non-steroidal anti-inflammatory drugs, warfarin, coumarin derivatives, platelet aggregation inhibitors) within 1 week prior to start of treatment for the first bleeding episode, or as a planned or expected medication during the time period from Day 1 until 24 hours (i.e., 1 day) after the last *Octafibrin* infusion

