Surgery analysis set (SURG): all documented surgical interventions with a need for at least one infusion of the IMP during the time period from the day of surgery until day of overall clinical assessment of post-operative efficacy in subjects of the FAS.

Surgery per protocol analysis set (SURG-PP): all surgeries of the SURG analysis set, where the patients underwent the surgery fulfil the following conditions:

- Provide valid, i.e., non-missing, intra- and post-operative efficacy data for the surgery
- Received  $\geq 90\%$  of the planned total dose of the IMP in the first infusion prior to the surgery
- Received  $\geq 80\%$  of the calculated dose (if no dose was calculated, 0% will be assumed) of the IMP over all further infusions of the surgery according to the treatment schedule
- Did not meet any of the following exclusion criteria:
  - Bleeding disorder other than congenital fibrinogen deficiency
  - End-stage liver disease (i.e., Child-Pugh-score B or C)
  - Suspicion of an anti-fibrinogen inhibitor as indicated by previous IVR, if available  $<0.5 \text{ (mg/dL)/(mg/kg)}$
  - Treatment with any fibrinogen concentrate or other fibrinogen-containing blood product within 2 weeks prior to start of treatment for the bleeding episode.

- Did not use any coagulation-active drug (i.e., non-steroidal anti-inflammatory drugs, warfarin, coumarin derivatives, platelet aggregation inhibitors) within 1 week prior to start of treatment for the first bleeding episode, or as a planned or expected medication during the time period from Day 1 until 24 hours (i.e., 1 day) after the last *Octafibrin* infusion

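### Three pre-treatment look-back tests in SURG-PP and the episode-level BLEED-PP run from the wrong event, so clean surgeries or later bleeds can be dropped

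*SAP*

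**What the plan says.** SAP 6.1 (Subject Disposition) gives the per-protocol sets as lists of conditions.

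- **SURG-PP** is made up of "all surgeries of the SURG analysis set, where the patients underwent the surgery fulfil the following conditions". One listed exclusion is "Treatment with any fibrinogen concentrate or other fibrinogen-containing blood product within 2 weeks prior to start of treatment for the bleeding episode". The drug condition looks back "within 1 week prior to start of treatment for the first bleeding episode".
- **BLEED-PP, episode level** covers "all documented bleeding episodes with no major protocol deviations, i.e. fulfilling the following conditions". Its drug condition opens with "The patient with the respective bleeding did not use any coagulation-active drug" but then looks back "within 1 week prior to start of treatment for the first bleeding episode". Its fibrinogen-product exclusion is "within 2 weeks prior to start of treatment for the bleeding episode".
- **FirstBLEED-PP** carries the same washout wording for each patient's first bleed. SAP 6.1 abbreviates this set as BLEED-PP too, so that label appears twice. This point concerns the second use.

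The drug condition has a second limb in all three sets: planned or expected use from Day 1 until 24 hours after the last Octafibrin infusion.

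Protocol 4.3, exclusion 4, sets the fibrinogen-product washout "within 2 weeks prior to start of treatment for the PK phase, a bleeding episode, or surgery" and the drug washout "within 1 week prior to start of the PK phase or treatment for the bleeding episode or surgery". Protocol 4.4.2 also dates the drug restriction from the bleed or surgery. Protocol 9.2.8 and 9.2.9 leave the details of BLEED-PP and SURG-PP to the SAP and ask only for criteria similar to those of FirstBLEED-PP.

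**The concern.** A washout test should look at the days before the event being classified. Three of the SAP's tests look at the days before a bleed that may be a different event: both look-backs in SURG-PP, and the drug look-back in the episode-level BLEED-PP. The washout lines appear to have been carried over from FirstBLEED-PP, where a first-bleed date is right. The dosing lines in SURG-PP were adapted to refer to the surgery; the washout lines were not.

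The per-protocol results for surgery and for all bleeds would then not test the protocol's own eligibility rule. These sets are in use: BLEED-PP appears in most of the bleeding tables, SURG-PP in the surgery listings, and SAP 6.1 defines the age subpopulations on both.

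**Working it through.** The plan states no figure to reproduce, so the check is a comparison of texts followed by date logic.

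**1. Unit and reference date for each set (SAP 6.1)**

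| Set | Unit classified | 2-week fibrinogen test runs from | 1-week drug look-back runs from |
|---|---|---|---|
| FirstBLEED-PP | first bleed | the bleed (fits) | first bleed (fits) |
| BLEED-PP, episode level | each bleed | the bleed (fits) | first bleed (does not fit bleed 2 onwards) |
| SURG-PP | each surgery | a bleed (does not fit) | first bleed (does not fit) |

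PK-PP dates its fibrinogen washout from its own event, the PK phase. In SURG-PP the text also does not say which bleed is meant if the child has had several.

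**2. Date logic for the drug look-back**

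Rule: a violation exists if 0 ≤ (reference day − drug day) ≤ 7. The days are assumptions: first bleed on day 50, surgery on day 200, drug not continued into treatment.

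- (a) Drug on day 197 only. As written: 50 − 197 = −147, no violation, surgery kept. Dated from the surgery: 200 − 197 = 3, excluded.
- (b) Drug on day 47 only. As written: 50 − 47 = 3, surgery excluded. Dated from the surgery: 200 − 47 = 153, kept.
- (c) Drug on day 197, child never bled. As written: no reference day, so the look-back cannot be evaluated. Dated from the surgery: 3, excluded.

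Cases (a) and (b) apply equally to a later bleed on day 200 in the episode-level BLEED-PP. Case (c) can arise because Protocol 3.2.3 lets children enter for elective surgery. The SURG-PP fibrinogen test behaves in the same way with a 14-day window.

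**3. Several bleeds in one child (assumed: 4 bleeds, one drug violation)**

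- Violation before bleed 1 only: the listed criteria remove 4 of 4 episodes; dated from each bleed they remove 1 of 4.
- Violation before bleed 3 only: the listed criteria remove 0; dated from each bleed they remove 1.

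**4. Weight of one case**

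The SAP plans Clopper-Pearson intervals for all bleeds, on BLEED and BLEED-PP (Table 14.2.16). The number of episodes is not given, so a range is assumed. If all n succeed, the lower 95% limit is 0.025^(1/n).

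- n = 6: 0.025^(1/6) = 54.1%; n = 5: 0.025^(1/5) = 47.8%. One clean success dropped costs 6.3 points.
- n = 10: 69.2%; n = 9: 66.4%. One dropped costs 2.8 points.

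For surgery, the stated minimum is 2 procedures, so one misclassified surgery changes the set from 2 to 1.

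**The case against.** The strongest reply is that other text catches the confounded cases. SAP 6.2 counts eligibility violations and forbidden co-medication under Protocol 4.4.2 as major deviations, and those protocol rules are dated from the bleed or surgery. Protocol 9.2.8 and 9.2.9 describe both sets as free of major deviations, and the note in 9.2.9 allows further exclusions agreed in writing before database closure. A reader might infer that a surgery covered by another concentrate a few days earlier would be reported as a per-protocol success. The documents do not support that: it passes the listed criteria but may still be removed. Removal is not certain either. The SAP's BLEED-PP text equates freedom from major deviations with its own list, and its SURG-PP text has no general major-deviation clause. This part of the reply therefore largely stands for cases wrongly kept. It does nothing for cases wrongly dropped, because no provision puts a clean case back.

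Two other strong readings are tempting. One is that SURG-PP has no working drug test for a child who never bled. In fact only the look-back loses its date; the limb starting on Day 1 still applies, and for surgery Day 1 is the day of surgery. The other is that, with 2 surgeries, half of a surgical estimate is at risk. The denominator arithmetic is right, but SAP 10.5 plans no confidence interval for surgery, the surgery efficacy outputs in SAP section 14 are listings, and Listing 16.2.6.3.2 shows each assignment with its reason. A misassignment would be visible.

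**Conclusion.** The point holds as a conflict between the SAP's listed criteria and the protocol's washout dates. Three look-back tests refer to a bleed that need not be the event being classified. A clean surgery or later bleed can be wrongly dropped, a confounded one can pass the listed criteria, and the two SURG-PP look-backs cannot be evaluated for a child who had surgery and no bleed.

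This is conditional. An error arises only if washout status differs between the reference bleed and the classified event, or if a surgical patient has no bleed. The documents do not show how often either will happen.

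The importance is minor to moderate. The study is descriptive throughout. The primary FirstBLEED analysis, the FirstBLEED-PP analysis and the 2-week test in BLEED-PP are unaffected. The shifts of 2.8 to 6.3 points in the lower limit rest on assumed counts of 10 and 6 bleeds, all successful.

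**What to change.** Before database lock, amend three phrases in SAP 6.1:

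- SURG-PP, fibrinogen product: count the 2 weeks back from the first Octafibrin infusion for the surgery being classified.
- SURG-PP, coagulation-active drug: count the 1 week back from that same infusion.
- Episode-level BLEED-PP, coagulation-active drug: replace the first bleeding episode with the respective bleeding episode.

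Keep the first-bleed date only in FirstBLEED-PP, and give that set its own label so that BLEED-PP names one set. These edits align the SAP with Protocol 4.3 and 4.4.2 and change no clinical rule.

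The wording costs little, but the data need a check. For bleeds, prior medication is on the pre-infusion list (Protocol 6.1.3.1). For surgery, the pre-operative list (6.1.4.1) does not name it, and Protocol 4.4.1 confines concomitant medication recording to the surgical observation period, which starts with the first Octafibrin dose. SAP 5.4 instead says recording runs throughout the trial. The sponsor should confirm that medication dates for the 2 weeks before each surgery are captured; otherwise the corrected SURG-PP tests cannot be applied reliably.

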### Subpopulations

Subpopulations based on the following categories will be examined:

- Severity of bleeding: minor versus major (subpopulations of the BLEED analysis set)
- Age 0 to <6 years versus 6 to <12 years (subpopulations of the BLEED-PP and the SURG-PP analysis set)

## 6.2 Major Protocol Deviations

Major protocol deviations will be assessed and listed as part of the database lock procedures prior to data analysis, and will include:

- Violation of inclusion or exclusion criteria
- Concomitant medication that may confound study results (see section “4.4.2 Forbidden Concomitant Therapy” of the protocol)
- Non-compliance issues raised by the investigator or sponsor
- Dosing errors (less than 80% or more than 120% of the planned dose of *Octafibrin*)
- Treatment errors (fibrinogen treatment with therapies other than *Octafibrin* used for bleeding events or surgeries other than for emergency reasons)

The specific exclusion criteria for the study populations described in section 5.1 will be assessed together with the major protocol deviations prior to data analysis.

A list of major protocol deviations and the reasons for exclusion of patients from a study population will also be included in the CSR.

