Patients should be treated with the investigational medicinal product (IMP) whenever possible. If, in the opinion of the investigator, a bleeding episode is not effectively stopped or surgical prophylaxis is not adequate after the recommended dose of *Octafibrin* has been administered, the subject may receive a different licensed fibrinogen concentrate (e.g., Haemocomplettan P®/RiaSTAP™) or whatever the investigator considers standard of care. The use of another licensed fibrinogen concentrate is also permitted in emergency situations, e.g., if the IMP is not available for the patient in time.

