#### **4.8 Subsequent Therapy**

In case the bleeding is not effectively stopped or surgical prophylaxis is deemed not to be adequate after the recommended *Octafibrin* dosing as judged by the investigator (see Section 5.4), the subject may receive a different licensed fibrinogen concentrate (e.g., Haemocomplettan P®/RiaSTAP™) or whatever the investigator considers standard of care.

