#### **9.2.9 SURG population**

The SURG population will include all surgical interventions with a need for at least one infusion of the IMP during the time period from the day of surgery until overall clinical assessment of haemostatic efficacy (third inclusion criterion; see Section 4.2) in subjects of the FAS.

A SURG-PP population comprising surgical interventions with no major protocol deviations will be defined in the SAP with criteria similar to the FirstBLEED-PP population.

**NOTE:** Any protocol deviations which will lead to the exclusion from an analysis population other than those mentioned above must be agreed upon in writing by the Sponsor and the study statistician, and in any case, before database closure.

The efficacy analysis for the primary endpoint will be performed with the data from the first bleeding event of each patient using the FirstBLEED population (ITT analysis) as the primary population and using the FirstBLEED-PP population (PP analysis) as a secondary population. An additional analysis will be performed for all bleeding events on the BLEED and BLEED-PP population. The primary analysis population for the PK analysis will be the PK-PP population.

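### SAP 6.2 calls protocol-permitted fibrinogen rescue after Octafibrin failure a major deviation, and the SAP leaves open whether rescued failures drop out of the all-bleeds per-protocol set

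*SAP*

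**What the plan says.** **Protocol.** Section 3.2 gives two permissions for another fibrinogen product. The first concerns inefficacy: "If, in the opinion of the investigator, a bleeding episode is not effectively stopped or surgical prophylaxis is not adequate" once the recommended dose has been given, then "the subject may receive a different licensed fibrinogen concentrate" or standard of care. The second is added to the first: "The use of another licensed fibrinogen concentrate is also permitted in emergency situations". Section 4.4.1 repeats both. Section 4.8 repeats the inefficacy permission: "In case the bleeding is not effectively stopped or surgical prophylaxis is deemed not to be adequate after the recommended" dosing, another licensed concentrate may be used.

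**SAP 6.2.** The major deviations include "Treatment errors (fibrinogen treatment with therapies other than *Octafibrin* used for bleeding events or surgeries other than for emergency reasons". Emergency use is the only exemption. The section adds that the exclusion criteria for the analysis populations are assessed together with the major deviations before analysis.

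**SAP 10.1 and 10.4.** A subject or episode given another fibrinogen product or cryoprecipitate between first infusion and efficacy assessment is set to 'none', unless the use is clearly documented as unrelated to IMP efficacy.

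**Per-protocol sets.** SAP 6.1 defines BLEED-PP as "all documented bleeding episodes with no major protocol deviations, i.e. fulfilling the following conditions", followed by a list covering efficacy data, dose received, certain exclusion criteria and coagulation-active drugs. Use of another fibrinogen product after Octafibrin is not on it. Protocol 9.2.8 also describes BLEED-PP by absence of major deviations. Protocol 9.2.9 does the same for surgery: "A SURG-PP population comprising surgical interventions with no major protocol deviations will be defined in the SAP". Both protocol sections add that the criteria are to resemble those of FirstBLEED-PP.

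**The concern.** Rescue for inefficacy is an outcome of treatment. The protocol allows it and the SAP's efficacy rules count it as failure. Section 6.2 nevertheless places it among treatment errors, because its exemption covers only the second of the protocol's two permissions.

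The label matters if it feeds a per-protocol set. Section 6.2 is the only place where the SAP lists major deviations, and BLEED-PP is described as having none. An analyst who starts from 6.2 would remove a rescued bleed; an analyst who works from the list in 6.1 would keep it as a failure. Under the first course, the failure itself brings about the removal, and the per-protocol success rate rises for that reason alone. Deviations are assessed at database lock in an open-label study, so the choice could be made with outcomes known.

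**Working it through.** **Step 1. Set the rules side by side.**

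| Situation after Octafibrin has been given | Protocol 3.2, 4.4.1, 4.8 | SAP 6.2 | SAP 10.1, 10.4 |
|---|---|---|---|
| Another fibrinogen product because Octafibrin did not work | Permitted | Major deviation (not exempt unless also an emergency) | 'None' |
| Another fibrinogen product in an emergency | Permitted separately (3.2, 4.4.1) | Exempt | 'None', unless documented as unrelated to efficacy |

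The first row is the conflict: permitted, scored as failure, and classed as an error.

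**Step 2. Trace the route to exclusion, set by set, in the SAP.**

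- FirstBLEED-PP (6.1): defined by a list only, with no reference to major deviations and no rescue item.
- SURG-PP (6.1): likewise defined by a list only.
- BLEED-PP (6.1): described by absence of major deviations, then equated through 'i.e.' with a list that omits rescue. Here the two readings diverge.
- Labelling: 6.1 also gives the abbreviation BLEED-PP to the first-bleed per-protocol set. Tables 14.2.12 and 14.2.13, which report first-bleed efficacy, are assigned to BLEED and BLEED-PP. Which definition governs them is therefore unclear.

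**Step 3. Size the effect if rescued bleeds are dropped.** The plan states no power or sample-size calculation, so there is no figure to reproduce.

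Inputs: at least 6 first bleeds (Protocol 9.1, SAP 5.3); a two-sided 95% Clopper-Pearson interval (SAP 10.1). The number of rescued bleeds is not in the documents and is assumed. All other bleeds are assumed successes unless stated.

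For x successes in n, the lower limit is the 0.025 quantile of Beta(x, n − x + 1) and the upper limit is the 0.975 quantile of Beta(x + 1, n − x). When x = n, the lower limit reduces to 0.025^(1/n) and the upper limit is 1. For example, 5/5 gives 0.025^(1/5) = 0.478.

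| Bleeds | Assumed rescued | Kept as 'none' | Dropped |
|---|---|---|---|
| 6 | 1 | 5/6 = 83.3% (35.9–99.6) | 5/5 = 100% (47.8–100) |
| 6 | 2 | 4/6 = 66.7% (22.3–95.7) | 4/4 = 100% (39.8–100) |
| 6 | 3 | 3/6 = 50.0% (11.8–88.2) | 3/3 = 100% (29.2–100) |
| 12 | 1 | 11/12 = 91.7% (61.5–99.8) | 11/11 = 100% (71.5–100) |
| 12 | 2 | 10/12 = 83.3% (51.6–97.9) | 10/10 = 100% (69.2–100) |

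Failures not given another fibrinogen product stay in. With 6 bleeds, one rescued failure and one failure without rescue, the comparison is 4/6 = 66.7% (22.3–95.7) kept against 4/5 = 80.0% (28.4–99.5) dropped.

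If the 6.1 list is exhaustive, 6.2 changes none of these figures.

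**The case against.** The strongest reply is that 6.2 is a reporting list and not part of any population definition. It says deviations are assessed and listed, and it treats the population criteria as a separate matter assessed alongside them. Its thresholds differ from those in 6.1: it flags doses under 80% or over 120% of plan, whereas the FirstBLEED-PP and SURG-PP lists require at least 90% for the first infusion and set no upper limit. Protocol 9.2.9 also requires written agreement before database closure for any exclusion not already named. This stands as a plausible reading, but the SAP does not say it is the intended one.

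Three stronger inferences are tempting, and the documents do not support them.

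- *That all per-protocol sets lose the treatment failures.* In the SAP only BLEED-PP carries the phrase about major deviations. The protocol's wording for SURG-PP continues with criteria similar to FirstBLEED-PP, which has no rescue criterion. Failures without another fibrinogen product are untouched in any case.
- *That the per-protocol support for the primary endpoint is compromised.* SAP 7 names FirstBLEED-PP for that analysis, and its list does not refer to major deviations. The exposure of Tables 14.2.12 and 14.2.13 rests on an ambiguous label.
- *That bleeds treated with another product because IMP was unavailable remain in while failures leave.* A bleed that never received Octafibrin is not in BLEED at all. If supply ran out during an episode, the condition of at least 80% of the calculated dose over further infusions might remove it. A patient switched for inefficacy might also miss that condition, independently of 6.2.

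**Conclusion.** The wording conflict is established: SAP 6.2 classes as an error what the protocol permits and what SAP 10.1 and 10.4 score as failure. Removal of rescued failures from BLEED-PP is one of two available readings, and the SAP does not choose between them. First-bleed Tables 14.2.12 and 14.2.13 may be affected through the shared label.

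Under the excluding reading, one assumed rescue among 6 bleeds with no other failure moves the observed rate from 83% to 100% and the lower 95% limit from 36% to 48%. The primary FirstBLEED analysis keeps rescued subjects as failures under either reading. The per-protocol analyses are secondary and all analyses are descriptive. This is a correction worth making before database lock, and no threat to the main result.

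**What to change.** Change the SAP wording only; the clinical rescue provisions stay as they are.

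1. In 6.2, limit the treatment-error item to use of another fibrinogen product that protocol 3.2, 4.4.1 or 4.8 does not permit.
2. In 6.1, state that fibrinogen rescue for lack of efficacy is an outcome scored 'none' and is not by itself a reason for exclusion from any per-protocol set. The other listed criteria continue to apply, so the statement must not be worded as an unconditional right to remain in the set.
3. State that the condition lists in 6.1, and not 6.2, define the per-protocol sets.
4. In 10.5, the rule that scores a switch during surgery as 'none' refers to another FIX product. Change this to another fibrinogen product; as it stands, the surgical rule does not cover the event in question.

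The cost is a short SAP amendment, and the per-protocol success rate may come out lower than it would if rescued bleeds were dropped.
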